4. TRIAL SCHEDULE

4.1. Study Visits and Procedures

(a) Visit 1 - Screening

Volunteers will be interviewed and screened by study personnel. If the volunteer satisfies the inclusion and exclusion criteria, a written informed consent will be obtained from all selected volunteers prior to their participation in the study. Volunteers will have the study explained to them by a study personnel, will read the consent form, have the opportunity to ask questions, and then sign the approved written Informed Consent form and keep a copy. The study personnel will then proceed to schedule visit 2 and 3 with the participant.

(b) Visit 2 - Installation of CGMS (Day 1)

Upon arrival, the participant will be educated on how to maintain and care for a CGMS and to keep a food and activity diary for the duration of the CGM. During this period (Day 1-14), participants will receive SMS to check on the CGMS. If there is a need, the research personnel will arrange for a mutually convenient time and place to review and replace the CGMS. Then, the participants will proceed to take the first MMTT.

Mixed meal tolerance test (MMTT)

Before the test, measurement of participants' height, BMI, waist and hip circumference, will be done and recorded. Next, participants will be asked to attend the MMTT protocol. The participant will need to fast (no food or drinks, except plain water) from 10 pm the night before or for approximately 10-12hr prior to the study visit. No food except clear water should be

consumed. A cannula will be inserted into the participant's forearm and the cannula will remain for blood sampling only. A fasting sample will be taken for the immediate measurement of glucose while other samples for insulin, gut hormones (GLP-1, GIP, Peptide YY, Ghrelin, and Glucagon), and other metabolites will be taken, processed, stored and analysed in batches at a later stage. Then, the participant will be given either mixed meal with controlled rice or mixed meal with test rice. At 0, 15, 30, 45, 60, 90, 120 minutes, blood will be sampled through a cannula from one of the arms. Subjects will be asked to remain seated throughout the visit and only minimal movement is allowed. Blood-taking will be conducted in room designated and approved for phlebotomy purposes. Only trained personnel and/or trained nurses will be conducting the blood drawn.

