6. STATISITCAL METHODS

The sample size was calculated based on Glycaemic Index Research Report #1719 conducted by Sydney University's Glycaemic Index Research Service on the 30% Fibre Grain replacement.

Based on the primary outcome of detecting a difference of 27 units in incremental area under the curve (iAUC) from 0 to 120 minutes (iAUC 0-120min) between control and 30% fibre enriched rice and a standard deviation of 25 units in iAUC 0-120min, calculations showed that with $\alpha = 0.05$, and power of 0.9, at least 21 subjects were needed. To account for possible subject attrition during the study, 25 subjects were recruited.

All data will be analyzed using statistical software (eg. SPSS/Stata), with significance defined as a p value of less than 0.05 on a 2-sided paired t-test. Other variables will be presented as mean \pm SE with differences between groups assessed by mixed model for categorical variables and continuous variables. Data will be explored for assessment of errors, missing values, and distribution of the variables. Evaluable subjects will be those who meet eligibility and have no missing values for calculating area under the curve (AUC). Variables that will be obtained include:

For CGM profile, paired t-test will be used to compare the fibre enriched rice meal and normal rice meal group in the following:

- a. Mean of interstitial glucose (IG) per 24 hours
- b. Postprandial peak IG (highest level after meal at breakfast, lunch and dinner)
- c. Postprandial time to peak IG (at breakfast, lunch and dinner)
- d. Mean amplitude of glycemic excursion (MAGE) to assess variability. This is determined by calculating arithmetic mean of the difference between qualifying consecutive peak and nadirs. Glucose excursions > 1 SD of the mean glucose concentrations will be included.

For postprandial glucose profile after the single meal:

- a. Plasma fasting and postprandial glucose (mmol/l), insulin (mU/l) and gut hormones.
- b. The incremental AUC (0-2h) will be derived from the glucose concentration profile during the meal test (defined as the area under the glucose curve that is over the basal value taken at time). Differences between the two meals will be analyzed by paired t-test

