10.2. Statistical and Analytical Plans

a. General Considerations

All data will be analyzed using statistical software (eg. SPSS/Stata), with significance defined as

a p value of less than 0.05 on a 2-sided unpaired t-test. Other variables will be presented as mean \pm SE with differences between groups assessed by mixed model for categorical variables and continuous variables. Data will be explored for assessment of errors, missing values, and distribution of the variables.

b. Safety Analyses

Safety analysis for adverse events will be performed every visit.

c. Interim Analyses

No interim analysis has been planned for this study.

d. Describe the types of statistical interim analyses and stopping guidelines (if any) that are proposed, including their timing.

All data taken up to that time point will be analysed including incidence of adverse events.

Decision for stopping of study will be in accordance with the adverse events reporting.

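### The insulin and gut hormone comparisons make no stated use of the fasting value drawn before each test meal, so removable visit-to-visit variation stays in the error of these secondary endpoints

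*Combined protocol and SAP*

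**What the plan says.** Section 4.1 (b) provides for a pre-meal draw at the MMTT: "A fasting sample will be taken for the immediate measurement of glucose while other samples for insulin, gut hormones (GLP-1, GIP, Peptide YY, Ghrelin, and". The hormone list is completed by glucagon. Further samples follow up to 120 minutes. Section 4.1 (d) applies the same procedure on Day 14. Each analyte therefore has its own fasting value at both tests.

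In Section 6, the single-meal list has two items. Item a names "Plasma fasting and postprandial glucose (mmol/l), insulin (mU/l) and gut hormones". Item b defines an incremental AUC above the basal value, from the glucose curve only, and compares it by paired t-test. For variables other than the primary, Section 6 says: "Other variables will be presented as mean \pm SE with differences between groups assessed by mixed model for categorical variables and continuous variables". It names no time structure, no covariate and no baseline rule. Section 10.2 repeats the mixed-model sentence and adds none.

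The two sections also disagree on the t-test. Section 6 has "a p value of less than 0.05 on a 2-sided paired t-test" and Section 10.2 has "a p value of less than 0.05 on a 2-sided unpaired t-test". That needs reconciling separately. The working below takes the within-person comparison of Section 6, which fits the crossover design.

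**The concern.** A sample drawn before a meal cannot be affected by that meal. Its use in an acute meal comparison is as a baseline, because a person whose insulin or GLP-1 starts higher on one visit may also run higher after eating on that visit. The crossover removes stable differences between people, but not this within-person shift between Day 1 and Day 14. The plan measures the shift for every analyte and states no use for it.

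At stake is the chance of detecting a real difference in insulin or gut hormones between the meals in some 20 to 25 people. There is also a question of pre-specification. The text leaves several defensible hormone analyses open, and they can give different answers.

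**Working it through.** **1. The plan's own figure.** Section 6 bases its sample size on "detecting a difference of 27 units in incremental area under the curve (iAUC) from 0 to 120 minutes" and "a standard deviation of 25 units in iAUC 0-120min", and concludes with "power of 0.9, at least 21 subjects were needed". If 25 is the SD at each meal and the two meals are uncorrelated, the SD of the difference is 25 × √2 = 35.4. A two-sided paired t-test at 0.05 then has power 0.899 at n = 20 and 0.914 at n = 21, so 21 is reproduced. (If 25 were the SD of the paired difference, 12 would suffice.) The figure concerns glucose iAUC, which already uses the basal value, so this point does not change it. It supplies n = 21 below.

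**2. Set-up for insulin and each hormone.** Let D be a person's difference between meals in the postprandial summary, F the same person's difference in fasting value, and ρ the correlation of D and F. Adjusting for F leaves variance (1 − ρ²) × Var(D). The documents give no SD or ρ for any of these analytes, so ρ is an assumed range and 80% unadjusted power is a chosen reference.

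**3. Power.** At n = 21 (20 df, two-sided 0.05), 80% power needs a noncentrality λ = 2.945. After adjustment it is λ/√(1 − ρ²) with 19 df.

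| ρ | 1 − ρ² | λ/√(1 − ρ²) | Power, df charged | Power, slope estimation also charged |
|---|---|---|---|---|
| 0 | 1.00 | 2.945 | 79.8% | 77.6% |
| 0.2 | 0.96 | 3.006 | 81.4% | 79.3% |
| 0.3 | 0.91 | 3.088 | 83.4% | 81.3% |
| 0.4 | 0.84 | 3.214 | 86.2% | 84.3% |
| 0.5 | 0.75 | 3.401 | 89.7% | 88.1% |
| 0.6 | 0.64 | 3.682 | 93.7% | 92.5% |

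The fourth column charges only the lost degree of freedom, and by that reckoning the cost at ρ = 0 is 0.2 points. It is the same to within 0.001 at n = 20 and n = 25. The last column also multiplies the variance by 1 + 1/(n − 3) = 19/18 = 1.056, the average price of estimating the slope when F is normal with mean zero. Simulation agrees with it to within 0.2 points. On that stricter count, adjustment breaks even between ρ = 0.2 and 0.3.

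**4. If time 0 were pooled.** Suppose the model averaged time 0 equally with the six samples from 15 to 120 minutes into one meal effect. With a constant effect after the meal and none before it, the estimate would be 6/7 = 0.857 of the true effect, a shrinkage of 1/7. If the paired differences also had a common correlation of 0.2 to 0.5 across times, power would fall from 80% to 68–70%. With trapezoidal weights, time 0 counts for only 7.5/120 = 6.25%. Where the overall contrast uses post-meal samples only, there is no shrinkage.

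**5. Simple change from fasting.** With k the SD of F divided by the SD of D, the variance relative to no adjustment is 1 + k² − 2ρk. This is below 1 only if ρ > k/2. At k = 1 and ρ = 0.3 it is 1 + 1 − 0.6 = 1.4, so subtraction would lose precision.

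**6. Form of the covariate.** In a random-intercept model with the raw fasting value, the fitted slope b mixes the between-person and within-person slopes. With within-person slope w, the adjusted difference has variance equal to the residual variance plus (b − w)² × Var(F). Unadjusted, the added term is w² × Var(F). For positive w, such a model is therefore worse than no adjustment once b exceeds 2w. In a simulated example with 21 people, an assumed between-person slope of 1.5 and within-person slope of 0.3, the SD of the meal estimate was 0.40 with this model, 0.30 with the within-person regression and 0.30 unadjusted.

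**The case against.** The strongest reply is that the plan is silent rather than wrong. Item a is a list of variables to be obtained, and the mixed-model sentence excludes no covariate. That stands in part. A reader might infer that fasting values are formally tested as meal outcomes, or that time 0 enters an averaged meal effect and dilutes it. The documents support neither. Comparisons at each time, a meal-by-time model or a post-meal average would all fit the text, so the shrinkage in step 4 is conditional.

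Second, the gain may be small. The crossover already removes stable differences between people, and at ρ of 0.2 to 0.3 the gain is at most one to three points, or roughly nil on the stricter count. That stands, and it limits the weight of the point.

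Third, the Day 14 fasting sample follows about 13 days of delivered meals, with the rice switched after day 7, while the Day 1 sample precedes them. Its value may partly reflect diet. This does not defeat adjustment for the acute effect, because the sample still precedes that visit's test meal. It does mean that the fasting difference should not be treated as pure noise, and that fasting values deserve their own report.

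Fourth, the hypothesis and the sample size concern glycaemic response, and the primary outcome is already baseline-referenced. That is correct. A reader might go further and infer that the hormone results favour one rice. Randomised meal order gives no ground for that.

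**Conclusion.** The point holds as a loss of precision in the secondary insulin and gut hormone comparisons, together with an unstated role for the fasting value. It is not a bias, and the primary glucose iAUC and its sample size are unaffected.

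The size depends entirely on ρ, which the documents do not give. From 80% unadjusted power at n = 21, adjustment gains little at ρ = 0.2, about 4 to 6 points at 0.4 and about 12 to 14 points at 0.6, depending on whether slope estimation is charged. At ρ = 0 it costs 0.2 points from the degree of freedom alone, or about 2 points on the stricter count. The 1/7 shrinkage applies only if time 0 is pooled with equal weight into one overall meal effect, which no section states. The change is worth making because the samples are already planned and the choice is best fixed before the data are seen.

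**What to change.** In Section 6, for insulin and each gut hormone:

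- Name one post-meal summary as the outcome (mean or AUC over 15–120 minutes), and leave time 0 out of the overall meal contrast.
- Adjust for the within-person fasting difference in the same analyte. Three forms do this: regress the within-person postprandial difference on the within-person fasting difference with a visit (period) term; fit a model with fixed participant effects; or fit a random-intercept model that also includes the participant's mean fasting value. A random-intercept model with the raw fasting value alone is not equivalent.
- Do not use simple change from fasting.
- Report fasting values by visit, separately from the acute meal effect, since the Day 14 sample follows the study meals.

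Carry the same wording into Section 10.2.

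The cost is SAP text, with no new samples, visits or participants. The downside is one degree of freedom per analyte, the small price of estimating the slope, and the loss of participants for any analyte whose fasting value is missing.

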At each time point, the participant will also be given a visual analogue scale (VAS) to indicate how they feel in response to given statements by marking an "X" on a 100-mm line. For example, "How strong is your desire to eat? " Response: Very weak (0 mm) to very strong (100 mm). Appetite was evaluated using a 100 mm VAS. At time 15 min, palatability of the treatment will be assessed by five characteristics, from bad (0 mm) to good (100 mm). These characteristics were visual appeal, smell, taste, texture, and overall pleasantness of the meal given. Scores were determined by measuring the distance (in mm) from the left starting point of the line to the intersection of the "X". The average scores and AUC will be calculated and compared between the two meals

(c) Continuous glucose monitoring (Day 1 - 14)

For the next 14 days, participants will be provided with lunch and dinner from the research team through delivery. They will be randomized to receive either mixed meal with controlled rice or mixed meal with Fibre Grain rice for day 1 to 7 and received the alternative for the day 8- 14. Participants will not be told whether they are receiving the Fibre Grain rice or control rice

(d) Visit 3 (Day 14 of CGM) – MMTT2 and removal of CGMS

On day 14, participants will return to undergo the second MMTT. Their height, BMI, waist and hip circumference will be measured and recorded. Participants will be asked to attend the same MMTT protocol (refer to Day 1 – MMTT protocol). Lastly, they will return the CGMS, and your 14-day food and activity diary

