5. STUDY DESIGN

This study is a within-subject cross-over trial design to assess the glycemic response of fibre enriched rice consumer by human subjects as compared to normal non-enriched rice in a mixed meal setting. The approximate time to complete study recruitment will be 4 weeks. Generally healthy population will be recruited in this study. There will be 3 visits in total (including screening). Each visit last from 3-4 h. During the visit, the participants are required to undergo a mixed meal tolerance test and carry a continuous glucose monitoring system for the next 14 days. The meals will be prepared by caterer in the morning of the test and send to the participants. The participant's glycemic response to control (normal rice) will be compared to their response after consumption of fibre enriched rice in a mixed meal setting. A reduction in postprandial blood glucose response will show that Fibre Grain rice is effective in improving the glycemic response of a meal.

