6.1. Randomisation and Blinding

Participants will be randomized to receive either mixed meal with Fibre Grain or mixed meal

with control rice for the first MMTT (visit2) and the alternative for the second MMTT (visit3). They will also be randomized to receive either Fibre Grain meal or Jasmine rice in mixed meal during CGM. It will be a single blinded trial as participants will not be told whether they are receiving the Fibre Grain or control white rice.

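### The crossover endpoints are tested without a period term or stated sequence balance, and section 10.2 names an unpaired test instead of the paired one

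*Combined protocol and SAP*

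**What the plan says.** Section 5 sets the design: "This study is a within-subject cross-over trial design to assess the glycemic response of fibre enriched rice". Section 6 makes iAUC 0-120 min the primary outcome and says: "Differences between the two meals will be analyzed by paired t-test". For the CGM profile it says "paired t-test will be used to compare the fibre enriched rice meal and normal rice meal group". Neither analysis has a period or sequence term, and the mixed model given for other variables names none.

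On timing, section 4.1(b) has the sensor fitted on Day 1: "Then, the participants will proceed to take the first MMTT". Section 4.1(c) supplies one rice "for day 1 to 7 and received the alternative for the day 8- 14". Section 4.1(d) adds: "On day 14, participants will return to undergo the second MMTT".

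Section 6.1 randomises which meal comes at the first MMTT and then says: "They will also be randomized to receive either Fibre Grain meal or Jasmine rice in mixed meal during CGM". It gives no allocation ratio or blocking, and does not say whether the two orders are independent.

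Section 10.2 defines significance as "a p value of less than 0.05 on a 2-sided unpaired t-test", where section 6 specifies a paired test.

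**The concern.** In a two-period crossover, any change between periods that has nothing to do with the meal enters the within-subject differences with opposite signs in the two sequences. If the sequences are balanced, it largely cancels from the mean but inflates the variance that the paired t-test uses. If they are unbalanced, part of it stays in that trial's estimate.

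The schedule gives a reason to allow for such a change. The first MMTT comes before any supplied rice, and the second falls inside the second rice week. The CGM comparison sets the first week of wear against the second.

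Two further points are left open. If the MMTT and CGM orders were tied, the meal at the second MMTT would be aliased with the rice eaten in week 2, and no model term could separate them. And the unpaired test in section 10.2 would discard the pairing that the crossover provides.

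**Working it through.** **Inputs from section 6:** difference 27 units, SD 25 units, two-sided alpha 0.05, power 0.9, at least 21 subjects, 25 recruited. Section 3.6 gives a minimum of 20. The plan does not say whether 25 is the SD of one measurement or of the within-subject difference.

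**Reproducing the plan's figure.** If 25 is the SD per measurement and the within-subject correlation is zero, the SD of the difference is 25 × √2 = 35.4. The two-sided paired t-test (noncentral t) then has power 0.899 at n = 20 and 0.914 at n = 21, so 21 is reproduced. If 25 is the SD of the difference, 12 subjects suffice and power at 21 is 0.997. Both readings are carried forward.

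**Model.** The shift s is the change in iAUC from the first to the second MMTT for the same meal. The documents give no value, so 5 to 20 units is an assumption. The test-versus-control difference for subject i is 27 ± s plus normal error, with the sign set by sequence.

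- Paired t-test: the mean difference is 27 + s(n1 − n2)/n, and the variance estimate is inflated by the spread between sequences. Power comes from a normal mean over an independent noncentral chi-square variance.
- Period-adjusted test: the average of the two sequence means, SE = SD × √((1/n1 + 1/n2)/4), with n − 2 degrees of freedom. It does not depend on s.

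**Near-balanced sequences, n = 21 (11/10).** Ranges cover the two directions of shift.

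| Shift | Paired power, SD 35.4 | Paired type I error, SD 35.4 | Paired power, SD 25 |
|---|---|---|---|
| 5 | 0.906-0.915 | 0.048 | 0.996-0.997 |
| 10 | 0.890-0.910 | 0.042 | 0.994-0.996 |
| 15 | 0.863-0.898 | 0.035 | 0.988-0.994 |
| 20 | 0.825-0.878 | 0.026 | 0.975-0.989 |
| Period-adjusted, any shift | 0.912 | 0.050 | 0.997 |

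**All 25 completing (13/12), SD 35.4.** Paired power is 0.941-0.953 at 10 units and 0.899-0.932 at 20, against 0.955 adjusted.

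**Simple randomisation, n = 21, SD 35.4.** Averaged over Binomial(21, 0.5) splits, the paired test's type I error is 0.050 at every shift examined. Its power is 0.914 at no shift, 0.909 at 5 units and 0.893 at 10. The adjusted test has 0.897 throughout.

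**A given imbalance.** A split of 14:7 or worse has probability 2 × P(X ≤ 7 | 21, 0.5) = 0.19. At exactly 14:7 the paired estimate moves by (14 − 7)/21 = one third of the shift. Conditional on that split, type I error is 0.061 at 10 units and 0.083 at 20 (SD 35.4). With 25 subjects, 16:9 or worse has probability 0.23, and at 16:9 the estimate moves by (16 − 9)/25 = 0.28 of the shift.

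**Tied orders.** A model for the MMTT data with intercept, treatment, period, sequence and week-2 rice at the second MMTT has five columns. Its rank is 5 when all four order combinations occur, and 4 when the CGM order is fixed by the MMTT order.

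**Unpaired test, no shift, n = 21.** At zero correlation nothing is lost (power 0.927, against 0.914 paired). At correlation 0.5 its type I error is 0.008 and its power 0.978, against 0.050 and 0.997 for the paired test.

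**The case against.** The strongest reply is that the paired test is legitimate here. Order is randomised, so overall type I error holds under simple randomisation, and with balance the test is conservative. On that view the period term buys only efficiency, under shifts that nobody has documented. At 5 units there is essentially no loss, and visible losses need 15 to 20 units, which is 56% to 74% of the 27-unit effect. They also rely on the SD reading with zero within-subject correlation. If all 25 subjects complete, power stays at about 0.90 or above throughout the range. The 14:7 error rates are conditional on one split and are not an overall risk. Under simple randomisation the term costs power at small shifts, and section 6 already writes of recruitment in the past tense, so blocking may come too late. Finally, section 10.1 refers to anthocyanin-fortified bread and a different sample, so the unpaired wording looks like leftover text.

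Most of this stands, and it limits the size of the point. It does not remove it. The SD reading that reproduces 21 leaves little margin above 0.90, and section 3.6 accepts 20 subjects. With 25 completers the gain is smaller but still present. Leftover or not, section 10.2 is current text and contradicts section 6. The aliasing matter needs only clarification, since section 6.1 reads most naturally as two separate randomisations.

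**Conclusion.** The concern holds, at a modest size. The paired analysis is not invalid and does not raise the overall false-positive rate. What is at stake is up to about 2 points of power at an assumed 10-unit shift and about 3 to 9 points at 20 units (n = 21, near-balanced, SD of the difference 35.4). If 25 is the SD of the difference, the loss is about 2 points at most. Without stated balance, the estimate from the actual trial also depends on the realised split. These sizes rest on assumed shifts and on which SD reading is right. The conflict between sections 6 and 10.2 over the test depends on no assumption and has to be resolved. The change should be made because it is cheap and specific.

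**What to change.** - Analyse iAUC 0-120 min and each CGM endpoint with fixed treatment, period and sequence and random subject. Equivalently, compare the period differences between sequences by a two-sample t-test. Name this as the single primary test, and replace the unpaired wording in section 10.2 so that it agrees with section 6.
- Allocate in balanced blocks over the four combinations of MMTT order and CGM order, and state that the two orders are independent. Week-2 rice can then be an optional covariate at the second MMTT.
- If allocation has already taken place, report how it was done and the realised split, and fix the analysis wording before the data are analysed.

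The cost is SAP wording and a blocked list, with no extra participants or procedures. The period term uses one degree of freedom. With no period effect, power goes from 0.914 to 0.912 if sequences are balanced, but from 0.914 to 0.897 under simple randomisation, where the term only about breaks even at a 10-unit shift (0.893 paired, 0.897 adjusted). The term and the balanced allocation should therefore be adopted together.
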